2.2 Background

Globally, cervical cancer is one of the most common and lethal gynecologic cancers. Advanced/metastatic disease is typically treated with chemotherapy, often with poor response rates and durations of response (DOR).

Improved treatment options are needed for patients with advanced cervical cancer:

- Currently, platinum-containing chemotherapy regimen with or without bevacizumab is the standard first-line therapy for patients with metastatic cervical cancer. In patients with locoregionally advanced cervical cancer, concurrent platinum-containing chemotherapy in combination with radiation therapy is recommended ([Monk 2007](#)).
- Despite a large series of tested treatment options for patients following standard of care first-line treatment, there is no established consensus for second-line treatment. Treatment options are limited due to low response rates that are typically short-lived and associated with variable toxicities ([McLachlan 2017](#); [Monk 2007](#)).

A literature review of clinical studies reporting efficacy outcomes for systemic anticancer treatments in platinum-experienced patients with locally advanced or metastatic cervical cancer led to the identification of 59 relevant publications reporting results on 1,943 patients with platinum-experienced cervical cancer. The majority of studies reported meager response rates with a median reported ORR of 10%. A random-effect model to account for heterogeneity between studies estimated the ORR across all selected publications at 15% (95% CI: 12.4%, 18.2%). In addition to this limited response the weighted average median OS and PFS times were 8.3 and 3.3 months respectively.

In addition to the low response rates, responses were short in duration when they were reported (15 studies): median DORs ranged from 1.6 to 13.9 months (13.9 months duration was reported in a study of temsirolimus with a single partial responder among 33 patients evaluable for response), and 12 studies (80%) reported median durations of responses of 6.2 months or less ([Tinker 2013](#)).

Nivolumab was the first PD-1 inhibitor with reported efficacy data in cervical cancer. In Checkmate-358, 19 patients with recurrent and/or metastatic cervical cancer were treated, and an ORR of 26.3% (95% CI: 9.1, 51.2) was observed ([Hollebecque 2017](#)). Neither DOR, nor proportion of treated cervical cancer patients naïve to systemic chemotherapy were reported.

Pembrolizumab is the first checkpoint inhibitor that received approval (accelerated) from the FDA in 2018 for use as monotherapy treatment of patients with recurrent or metastatic cervical cancer with disease progression on or after chemotherapy whose tumors express PD-L1. This approval was based on the interim results from the Phase II KEYNOTE-158 study ([Chung 2019](#)):

- Among the 98 patients with previously treated advanced cervical cancer, the ORR was 12.2% (95% CI: 6.5%, 20.4%), median PFS was 2.1 months (95% CI: 2.0, 2.2 months), and median OS was 9.4 months (95% CI: 7.7, 13.1 months).

- Among the 77 patients with PD-L1 positive (CPS \geq 1), chemotherapy refractory cervical cancer, the ORR was 14.3% (95% CI: 7.4, 24.1). At the time of the publication, median DOR was not reached (range 4.1 to 18.6+ months), and median OS was 11 months (95% CI: 9.1, 14.1).
- In KEYNOTE-158, no responses were observed among the PD-L1 negative patients (CPS < 1, n=15), and 3 patients experienced best overall response as stable disease.

While the overall response rates with pembrolizumab are only comparable to other treatment options for cervical cancer patients (12.2% to 14.3%), the durability of responses are noteworthy and have presented immunotherapy as a promising treatment for this disease.

Recently, molecular characterization of cervical cancer by The Cancer Genome Atlas identified both PD-L1 and TGF- β signaling as frequently dysregulated in this disease ([The Cancer Genome Atlas Research Network 2017](#), [Roszik 2018](#)). TGF- β is historically known to be expressed in a majority of cervical cancer tissues, and its expression correlates with the extent of tumor stroma infiltrate ([Hazelbag 2002](#)). Furthermore, the role of TGF- β in cervical cancer pathogenesis is supported by data including 1) TGF- β 1 upregulation by human papilloma virus (HPV) oncoprotein E6 and E7 ([Peralta-Zaragoza 2006](#)), and 2) the correlation of poor prognosis in cervical cancer and the expression of plasminogen activator inhibitor-1, a molecule strongly and dose-dependently induced by TGF- β ([Hazelbag 2004](#)).

Bintrafusp alfa has shown promising clinical activity with durable responses in patients with chemotherapy refractory cervical cancer in Phase I study EMR200647-001. In the Phase I study, a total of 25 patients with recurrent or persistent cervical cancer following standard of care treatment were treated for advanced disease. The median treatment duration was 9.6 (range 2.0 to 72.0) weeks. The results are summarized:

- ORR of 24.0% (95% CI: 9.4, 45.1) with 6 confirmed responses per Response Evaluation Criteria in Solid Tumors Version 1.1 (RECIST 1.1); 5/6 responses were ongoing at data cutoff (median DOR not reached; range 2.3+ to 24.9+ months).
- One additional participant developed a partial response (PR) after initial confirmed disease progression, bringing the total clinical response rate to 28.0% (95% CI: 12.1, 49.4). This additional participant's PR was ongoing for 8.7 months at data cutoff, with 73.3% disease shrinkage after initial progressive disease (PD).
- No clear relationship between PD-L1 protein expression and clinical response was observed. One patient with negative tumor PD-L1 expression (via 73-10 assay) had a confirmed PR.

Based on the biological rationale and promising clinical activity of bintrafusp alfa in cervical cancer and manageable safety profile in close to 700 participants with various cancer types (refer to IB), this study is designed to further investigate bintrafusp alfa in participants with advanced, unresectable, cervical cancer with disease progression during or after platinum-containing chemotherapy.

2.3 Benefit/Risk Assessment

At the time of study initiation, bintrafusp alfa demonstrated promising clinical efficacy in a cohort of participants with second-line (2L)+ cervical cancer in the Phase I study EMR200647-001, with a confirmed ORR of 24.0% and total clinical response rate of 28.0% (95% CI: 12.1, 49.4). The median DOR had not been reached by data cutoff - 5 of 6 responses were ongoing, with 1 ongoing response already lasting for > 2 years. These results demonstrate encouraging clinical efficacy of bintrafusp alfa in cervical cancer with favorable response rate and durability compared to historical benchmarks.

Platinum-containing chemotherapy regimen with or without bevacizumab is the standard first-line therapy for patients with metastatic cervical cancer. For patients with advanced unresectable and/or metastatic cervical cancer with disease progression during or after platinum-based chemotherapy there is no established consensus for second-line treatment options due to low response rates, typically short-lived and variable toxicities (Bookman 2000; Muderspach 2001; Schilder 2005; Alberts 2012). Based upon the poor clinical prognosis new treatment options for this patient population are needed, and these patients are included in the eligibility for this study (further rationale included in Section 4.2).

The identified and potential risks with bintrafusp alfa monotherapy were overall manageable and no new safety signals emerged in the Phase I studies (EMR200647-001, MS200647-0008) compared with therapies targeting PD-L1 or TGF- β . The following have been identified as important identified risks for M7824: Immune-related adverse events (immune-related pneumonitis, immune-related hepatitis, immune-related colitis, immune-related nephritis and renal dysfunction, immune-related endocrinopathies [thyroid disorders, adrenal insufficiency, Type 1 Diabetes mellitus, pituitary disorders], immune-related rash and other immune-related adverse events (irAEs) [myositis, myocarditis, encephalitis]), TGF- β inhibition mediated skin reactions, anemia and bleeding adverse events. The overall incidence and severity for irAEs is found to be consistent across bintrafusp alfa studies and similar to the known safety profile of approved anti-PD-L1 agents (Brahmer 2018).

Infusion-related reactions (IRRs) are classified as identified risk for the treatment with bintrafusp alfa. Infusion-related reactions observed with bintrafusp alfa were similar to those seen with monoclonal antibodies. At the time of study initiation, the overall bintrafusp alfa related IRRs were observed to be < 5%, of low-grade (Grade 1/2) severity and not requiring permanent treatment discontinuation.

Dermatologic AEs related to TGF- β -inhibition (including keratoacanthomas [KA] and cutaneous squamous cell cancers) are an important identified risk with bintrafusp alfa not seen with other PD-1/PD-L1 antibodies. These lesions were previously observed in participants with genetic mutations in the TGF- β receptor (i.e., Ferguson-Smith syndrome), and participants treated with the TGF- β -targeting agent fresolimumab (Goudie 2011; Morris 2014). At the time of study initiation, in the Phase I studies, treatment-emergent TGF- β inhibition mediated skin reactions were observed in approximately 11% of participants, and were well-managed with simple excision (or spontaneous resolution) and did not require any participant to discontinue treatment (refer to

IB). The risk of these lesions with bintrafusp alfa was considered manageable, especially in the context of encouraging clinical activity in several tumor types.

CCI

CCI

3 Objectives and Endpoints

Table 3 Study Objectives and Endpoints

Objectives	Endpoints
Primary	

 To evaluate clinical efficacy of bintrafusp alfa based on ORR 	
 Confirmed objective response according to RECIST 1.1 assessed by an IRC
Secondary	

 To evaluate clinical efficacy of bintrafusp alfa based on DOR 	
 DOR according to RECIST 1.1 assessed by an IRC

 To evaluate clinical efficacy of bintrafusp alfa based on DRR 	
 Durable response of at least 6 months according to RECIST 1.1 assessed by an IRC

 To evaluate clinical safety of bintrafusp alfa 	
 Occurrence of TEAEs and treatment-related AEs including AEs of special interest

 To evaluate clinical efficacy based on PFS 	
 PFS according to RECIST 1.1 assessed by an IRC

 To evaluate ORR, DOR, DRR, and PFS by Investigator read 	
 Confirmed objective response, DOR, DRR, and PFS according to RECIST 1.1 assessed by Investigator

 To evaluate clinical efficacy based on OS 	
 OS

 To characterize the PK profile of bintrafusp alfa 	
 The concentration observed immediately at the end of infusion (C_{EOI}) of bintrafusp alfa The concentration observed immediately before next dosing (corresponding to pre-dose or trough concentration [C_{trough}] for multiple dosing) of bintrafusp alfa

 To characterize the immunogenicity of bintrafusp alfa 	
 Immunogenicity of bintrafusp alfa as measured by ADA assay from Screening through Safety Follow-up visit (up to 28 days after last treatment)

 To evaluate clinical efficacy of bintrafusp alfa according to PD-L1 expression 	
 Efficacy endpoints by PD-L1 expression in tumor

ADA=antidrug antibody, AE=adverse event, DOR=duration of response, DRR=durable response rate, HPV=human papilloma virus, ir =immune-related, IRC=Independent Review Committee CCI [REDACTED] NCI-CTCAE v5.0=National Cancer Institute-Common Terminology Criteria for Adverse Events v5.0, OS=overall survival, ORR=objective response rates, PD-L1=programmed death-ligand 1, PFS=progression-free survival, PK=pharmacokinetic, CCI [REDACTED], RECIST 1.1=Response Evaluation Criteria in Solid Tumors Version 1.1, TEAE=Treatment-emergent adverse event, CCI [REDACTED].

4 Study Design

4.1 Overall Design

This is a Phase II, multicenter, international, single-arm study to evaluate bintrafusp alfa monotherapy in participants with advanced unresectable and/or metastatic cervical cancer with disease progression during or after platinum-based chemotherapy. See Section 5.1 and Section 5.2 for more details for the patient population.

The primary objective is to evaluate the clinical efficacy of bintrafusp alfa based on the ORR. The key secondary objectives are safety, DOR, durable response rate (DRR), PFS, and OS. The clinical efficacy of bintrafusp alfa will also be retrospectively evaluated according to PD-L1 expression.

The study plans to enroll approximately 135 eligible participants from multiple study sites globally. The Sponsor will monitor enrollment in the study and may make determinations to limit enrollment in certain countries and/or regions in order to obtain a study population representative of global standard of care, including prior bevacizumab treatment and representative enrollment across the participating global regions (for example, asian versus non-asian countries).

The study is intended to enroll at least 15% of participants from China. After reaching completion of the global study enrollment, if the number of participants enrolled in China does not meet the 15% target, enrollment may continue in China to meet local requirement until the target (at least 15%) participants from China is met.

CCI

The study includes:

- 28-day Screening period
- Treatment with bintrafusp alfa at a dose of 1200 mg once every 2 weeks until confirmed PD per RECIST 1.1, death, unacceptable toxicity, or study withdrawal.
 - In the case of PD, treatment may continue if the participant's performance status (PS) has remained at least stable, in the opinion of the Investigator, the participant will benefit from continued treatment, and if other criteria are fulfilled as outlined in the protocol (see Section 7.1.3).
 - Participants who have experienced a confirmed complete response (CR) should continue treatment for a maximum of 24 months after confirmation of response (at the discretion of the Investigator). If the Investigator believes that a participant with confirmed CR may benefit from treatment beyond 24 months, it may be permissible to continue treatment after discussion with the Medical Monitor and the Sponsor's Medical Responsible.
 - Patients with SD or PR should continue treatment until disease progression, or any other discontinuation criterion is met.
- Safety Follow-up will continue until 12 weeks after the last dose of bintrafusp alfa. The 12-week Safety Follow-up is allowed to be conducted via telephone calls or patient chart reviews unless there is a medical necessity requiring a clinical visit.
- Long-term Follow-up should be performed every 12 weeks after the Safety Follow-up according to the Schedule of Activities (see Table 1). Long-term Follow-up should be performed by chart reviews or telephone calls.
- Survival Follow-up will continue until the end of study as defined in Section 4.4. After stipulated end of study, Survival Follow-up may continue until the last participant has died or at the discretion of the Sponsor.

The overall study design is shown in Figure 1. A detailed Schedule of Activities (SoA) is provided in Section 1.3.

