
ADA=antidrug antibody, AE=adverse event, DOR=duration of response, DRR=durable response rate, IRC=Independent Review Committee, NCI-CTCAE v5.0=National Cancer Institute-Common Terminology Criteria for Adverse Events v5.0, OS =overall survival, PD-L1=programmed death-ligand 1, ORR=objective response rates, PFS=progression-free survival, PK=pharmacokinetic, RECIST 1.1=Response Evaluation Criteria in Solid Tumors Version 1.1, TEAE=Treatment-emergent adverse event.
	

Overall Design: This Phase II, multicenter, international, single-arm study is to evaluate bintrafusp alfa monotherapy in participants with advanced unresectable and/or metastatic cervical cancer with disease progression during or after platinum-based chemotherapy.

The study plans to enroll approximately 135 eligible participants from multiple study sites globally. The study is intended to enroll at least 15% of participants from China. After reaching the completion of the global study enrollment, if the number of participants enrolled in China does not meet the 15% target, enrollment may continue in China to meet local requirement until the target (at least 15%) participants from China is met.

Participants will receive an intravenous (IV) infusion of bintrafusp alfa at a dose of 1200 mg over 1 hour (-10 minutes/+ 20 minutes, i.e., over 50 to 80 minutes) once every 2 weeks.

The study includes:

- 28-day Screening period.
- Treatment with bintrafusp alfa at a dose of 1200 mg once every 2 weeks until confirmed progressive disease (PD) per Response Evaluation Criteria in Solid Tumors Version 1.1 (RECIST 1.1), death, unacceptable toxicity, or study withdrawal.
 - In the case of PD, treatment may continue if the participant's performance status (PS) has remained at least stable, in the opinion of the Investigator, the participant may benefit from continued treatment, and if other criteria are fulfilled as outlined in the protocol (refer to Section 7.1.3).
 - Participants who have experienced a confirmed complete response (CR) should continue treatment for a maximum of 24 months after confirmation of response (at the discretion of the Investigator). If the Investigator believes that a participant with confirmed CR may benefit from treatment beyond 24 months, it may be permissible to continue treatment after discussion with the Medical Monitor and the Sponsor's Medical Responsible.

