7.1 Discontinuation of Study Intervention

Participants may be discontinued from study intervention for any of the following reasons, one reinitiating course of treatment may be allowed (see Section 7.1.2.1).

- A participant may discontinue from the study intervention at any time at his/her own request (i.e., withdrawal of consent), and without giving a reason.
- Occurrence of an exclusion criterion, which is clinically relevant and affects the participant's safety, if discontinuation is considered necessary by the Investigator and/or Sponsor.
- A participant may be discontinued at any time at the discretion of the Investigator for safety, behavioral, compliance, or administrative reasons (See Section 6.8 and 6.9 for TEAEs and AESIs that require treatment discontinuation).
- Confirmed PD per RECIST 1.1, with the exception that participants receiving treatment may continue past PD if the participant's ECOG PS has remained at least stable, and if in the opinion of the Investigator, the participant will benefit from continued treatment (See Section 7.1.3).
- Unacceptable toxicity.
- Some TEAEs and AESIs require withdrawal from treatment. See Section 6.8 and 6.9 for additional details.
- Drug must not be given to a known pregnant participant (refer to Appendix 3).
- Use of a prohibited concomitant drug, as defined in Section 6.5.2, where the predefined consequence is withdrawal from the study intervention.

The SoA specifies the data to collect at study intervention discontinuation and follow-up and any additional evaluations that need to be completed.

In case of discontinuation from the study intervention:

- The day of End-of-Treatment will correspond to the day of withdrawal (or within 7 days).
- An attempt should be made to perform all assessments scheduled for the End-of-Treatment visit if possible. If not possible, the most clinically relevant assessments and appropriate eCRFs for the End-of-Treatment visit should be prioritized as feasible.
- Participants will be asked to continue Safety and Survival Follow-up, which includes the collection of data on survival, patient-reported outcome (PRO) questionnaires, and subsequent

anticancer therapy. After completion of the follow-up period or after the End-of-Treatment visit, whichever is applicable, the appropriate eCRF section for Study Termination must be completed.

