7.1.3 Treatment Beyond Progression

7.1.3.1 Treatment Beyond Initial Progression

Participants will receive bintrafusp alfa as outlined in the SoA until disease progression. Bintrafusp alfa may continue past the initial determination of disease progression according to RECIST 1.1 as long as the following criteria are met:

- Treatment with bintrafusp alfa is ongoing
- No new unacceptable treatment or disease-related toxicity
- Tolerance of study interventions
- At least stable ECOG PS
- Treatment beyond progression will not delay an imminent intervention to prevent serious complications of disease progression (e.g., CNS metastases).

A radiographic assessment should be performed within 4 to 6 weeks of original PD to determine whether there has been a decrease in the tumor size, or continued PD. The assessment of clinical benefit should be balanced by clinical judgment as to whether the participant is clinically deteriorating and unlikely to receive any benefit from continued treatment with bintrafusp alfa.

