7.1.3.2 Treatment Beyond Confirmed Progression

After confirmed PD, if the Investigator feels that the participant continues to achieve clinical benefit by continuing treatment, the participant should remain on the study and continue to receive monitoring according to the SoA. The decision to continue treatment beyond confirmed PD should be discussed with the Medical Monitor and documented in the study records.

Participants who continue beyond progression will be evaluated for further tumor response as per the protocol schedule. Treatment should be discontinued permanently upon documentation of further, unequivocal, disease progression unless there are no alternative therapeutic options and the benefit-risk assessment is favorable in consultation between the Investigator and the Medical Monitor. In case of continuation of treatment beyond PD, treatment will be discontinued once any other criteria for withdrawal are met.

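### The progression stop rule for study drug is worded two ways, and the stable-ECOG condition is tied to confirmed PD in Protocol 7.1 but to initial PD in 7.1.3.1

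*Protocol*

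**What the plan says.** Several places make confirmed PD the end of dosing. The Synopsis gives drug "once every 2 weeks until confirmed progressive disease (PD) per Response Evaluation Criteria in Solid Tumors Version 1.1", and its paragraph on study duration repeats confirmed PD. Section 4.1 has it as "once every 2 weeks until confirmed PD per RECIST 1.1, death, unacceptable toxicity, or study withdrawal". Section 7.1 lists among the reasons for discontinuation "Confirmed PD per RECIST 1.1, with the exception that participants receiving treatment may continue past PD", provided that ECOG PS is at least stable and the Investigator expects benefit, with a reference to 7.1.3. SAP 13 also names confirmed progression.

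Other places do not use the word confirmed. Section 7.1.3.1 opens with "Participants will receive bintrafusp alfa as outlined in the SoA until disease progression" and goes on: "Bintrafusp alfa may continue past the initial determination of disease progression according to RECIST 1.1 as long as the following criteria are met". At least stable ECOG PS is one of those criteria. For participants in SD or PR, 4.1 says "Patients with SD or PR should continue treatment until disease progression", and the Synopsis has a matching bullet.

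Section 7.1.3.2 covers the next stage: "After confirmed PD, if the Investigator feels that the participant continues to achieve clinical benefit by continuing treatment", the participant stays on study, and the decision is to be discussed with the Medical Monitor. ECOG is not named there.

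Directly under the treatment line in both 1.1 and 4.1, a sub-bullet allows treatment to go on in the event of PD if performance status is at least stable, the Investigator sees benefit, and the Section 7.1.3 criteria are met. It does not say whether this means initial or confirmed PD.

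**The concern.** A site needs to know which scan ends dosing and at which scan the performance-status test applies. Read from 7.1, the test comes at confirmed PD. Read from 7.1.3.1, it comes at the first PD. The two readings part for a participant whose first PD is not yet confirmed and whose ECOG PS has worsened.

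At stake are further infusions in a participant who is getting worse, and comparable exposure and safety data across sites. The situation need not be rare. Protocol 2.2 quotes median PFS of 2.1 and 3.3 months for other treatments in this setting, so progression is likely to be a common reason for reaching this decision.

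**Working it through.** The plan gives no figure on this point to reproduce. The check sets the passages side by side, applies one case to them, and then sizes the gap.

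**Step 1. The passages**

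| Place | What ends dosing | Where the performance-status condition sits |
|---|---|---|
| Protocol 1.1 and 4.1, treatment bullet | Confirmed PD | Sub-bullet: PD of unstated kind; PS at least stable; refers to 7.1.3 |
| Protocol 1.1, duration paragraph | Confirmed PD | Past radiologic progression only if stable and not clinically worsening; kind of PD unstated |
| Protocol 1.1 and 4.1, SD/PR bullet | Disease progression | None |
| Protocol 7.1 | Confirmed PD, in a list of permitted reasons | On confirmed PD |
| Protocol 7.1.3.1 | Disease progression | On the initial determination |
| Protocol 7.1.3.2 | Further unequivocal progression, for those who continue | ECOG not named; Medical Monitor discussion |
| SAP 13 | Confirmed progression | None |

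**Step 2. The case: ECOG 1 at entry, ECOG 2 at a first, unconfirmed PD**

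- Entry requires ECOG 0 to 1 (Protocol 5.1), so this is a worsening.
- Section 7.1: the PD item has not been reached, because PD is not confirmed.
- Section 7.1.3.1: the criteria for passing the initial determination are not met, because ECOG is not stable.
- Sub-bullets in 1.1 and 4.1: if PD means initial PD, continuation is not permitted. If PD means confirmed PD, they do not yet apply.
- Section 6.8 does not settle it. It withholds infusions at ECOG 3 or above, until ECOG is 2 or below, within the text on Grade 3 treatment-related events. ECOG 2 is not caught.

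**Step 3. Size per affected participant**

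Inputs: repeat imaging within 4 to 6 weeks of the original PD (Protocol 7.1.3.1); 1200 mg every 2 weeks (Protocol 6.1); on-treatment period to last dose + 30 days, or + 90 days for irAEs, ended sooner by subsequent anticancer therapy (SAP 9.8); duration of treatment = (last dose − first dose + 14)/7 weeks (SAP 13).

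- Infusions: 4/2 = 2 to 6/2 = 3.
- Cumulative dose: 2 × 1200 = 2400 mg to 3 × 1200 = 3600 mg.
- Duration of treatment: 4 to 6 weeks longer.
- End of the on-treatment period, counted from first PD and assuming a dose on that day under the shorter reading: 30 days against 30 + 28 = 58 to 30 + 42 = 72 days. For irAEs: 90 days against 90 + 28 = 118 to 90 + 42 = 132 days.
- Relative dose intensity does not move if doses are on schedule. With n infusions the duration is 2n weeks, so intensity is 1200n/(2n/2) = 1200 mg per cycle under either reading.

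**Step 4. Efficacy endpoints**

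PFS and DOR run to the first documentation of PD or death (Protocol Table 12; SAP 14.2.4 and 14.2.8). Best overall response is assessed until documented progression (SAP 14.1.1). None of these definitions uses the dosing trigger.

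**The case against.** The strongest reply is that no passage orders continued dosing in this case. A reader might infer that such a participant is told both to continue and to stop; the documents do not support that. The sub-bullets in 1.1 and 4.1 require stable performance status and refer to 7.1.3, which covers both initial and confirmed PD. The Synopsis ties treatment past radiologic progression to the absence of clinical worsening. Section 7.1 lists reasons for which participants may be discontinued, and one of them is the Investigator's discretion for safety. A list of permitted stop reasons is not an instruction to dose on. All of this stands.

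It can also be argued that 7.1 and 7.1.3.2 are cumulative, so that stable ECOG and the Medical Monitor discussion both apply after confirmed PD. That reading is possible, but the text does not state it, and it leaves open whether the test also applies at initial PD.

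Three further inferences are not supported. The Until PD column of Table 1 is not a competing rule, since its dosing row refers to 4.1 for treatment duration. The lack of a general definition of confirmed PD in Appendix 9 does not show that the protocol has none, because the content of Section 8.1 is redacted. The number of participants affected cannot be estimated, because the documents do not say how often ECOG declines at first PD.

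**Conclusion.** The point holds as an internal inconsistency in a stop rule. The trigger is worded two ways, and the stable-ECOG condition is placed on two different events. Sites can reasonably differ on whether the continuation conditions apply at initial PD, at confirmed PD or at both.

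The difference is about 2 to 3 infusions per affected participant, with a matching shift of 4 to 6 weeks in treatment duration and in the end of the on-treatment windows. This assumes that dosing is on schedule, that the repeat scan falls 4 to 6 weeks after first PD, that one reading stops at first PD while the other doses up to the repeat scan, and that no new anticancer therapy closes the window sooner. The windows themselves remain properly defined, since they follow the actual last dose; what could vary between sites is when that dose falls.

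ORR, PFS and DOR are not affected. The matter bears on participant safety and on exposure and safety reporting. SAP 6.1 restricts the planned analyses to one at the 15 February 2022 cutoff, so the practical gain is for participants still on treatment and for a clear account in the study report.

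**What to change.** Reconcile Protocol 1.1, 4.1 (including the SD/PR bullets), 7.1, 7.1.3.1 and 7.1.3.2 with SAP 13:

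- State once which determination of PD ends dosing, and use the same words in every section.
- Give one set of conditions for dosing past initial PD and one for dosing past confirmed PD, and say for each whether ECOG PS is part of it.
- In the sub-bullets of 1.1 and 4.1, say whether initial or confirmed PD is meant.

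Which rule to adopt is for the sponsor to decide. The cost is wording in a protocol amendment or administrative letter and one sentence in the SAP, with no added participants or procedures.
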